2.5 FDA approval

On November 20, 2008, it was announced that the United States Food and Drug Administration (FDA) granted accelerated approval for eltrombopag (Promacta®) for the treatment of thrombocytopenia in patients with chronic immune (idiopathic) thrombocytopenic purpura (ITP) who have had an insufficient response to corticosteroids, immunoglobulins or splenectomy. The new drug application for eltrombopag was supported by the largest database of randomized clinical trial information on investigational therapies for chronic ITP patients. The approval of eltrombopag was supported by a unanimous decision by the FDA's Oncology Drugs Advisory Committee (ODAC) on May 30, 2008, in which the panel voted, 16-0 that eltrombopag demonstrated a favorable risk-benefit profile for the short-term treatment of patients with chronic ITP. The indication is based on data from the two pivotal studies (detailed above) in the short-term

treatment and one ongoing long-term treatment study of patients with chronic ITP (EXTEND). Eltrombopag is the first oral thrombopoietin (TPO) receptor agonist approved for adult patients with chronic ITP.

In January 2014 eltrombopag (Promacta) gained Breakthrough Therapy designation status from the FDA and Priority Review in April 2014. On August 26, 2014 the FDA approved the additional use of eltrombopag in patients with severe aplastic anemia who have had an insufficient response to immunosuppressive therapy. The approval was based on results from the clinical trial done at the NIH described above, 09-H-0154 (NCT00922883).

Eltrombopag has also received FDA approval for the treatment of thrombocytopenia in patients with chronic hepatitis C to allow the initiation and maintenance of interferon-based therapy.

2.6 Rationale for dose selection

Dose selection prior to January 8, 2015:

Eltrombopag 50 mg once daily has been selected as the starting dose for this study because this regimen has been safe and effective in increasing platelet counts in patients with ITP and this was the FDA's recommended starting dose for this patient population. A starting dose of 25 mg once daily in East Asian patients will be used. Modified dosing for subjects of East Asian heritage (i.e., Japanese, Chinese, Taiwanese and Korean) has been implemented for the following reasons. In healthy Japanese subjects, plasma eltrombopag $AUC_{(0-\tau)}$ was approximately 80% higher when compared to non-Japanese healthy subjects who were predominantly Caucasian. Similarly, in patients with ITP, plasma eltrombopag exposure was approximately 70% higher in East Asian (i.e., Japanese, Chinese, Taiwanese and Korean) subjects as compared to non-East Asian subjects who were predominantly Caucasian as higher drug exposure in East-Asian subjects has been observed. After two weeks, the dose can be increased by 25 mg per day every 2 weeks in incremental doses up to a maximum dose of 300 mg (East Asians 125 mg) once daily as detailed in the treatment plan (Section 5) based on the following considerations:

- In an ongoing open label study (NCT00358540), eltrombopag doses of 75 mg (n=10), 100 mg (n=6) and 150mg (n=2) have also been given to patients receiving adriamycin and ifosfamide (AI) for the treatment of advanced soft tissue sarcoma. Dose escalations to 300 mg are planned in this ongoing study. Eltrombopag is being dosed daily for 5 days before and 5 days after AI chemotherapy starting in Cycle 2. [There were 4 patients who were dosed at 100mg. Two of the four had improved numeric platelet counts at the nadir in the cycle that they received eltrombopag compared to the cycle without eltrombopag. All had higher prechemotherapy platelet counts in Cycle 2 (with eltrombopag) compared to Cycle 1 (no eltrombopag). The one subject dose at 150mg did not take the tablets according to instructions]
- In healthy subjects, a clear dose and exposure response was seen for eltrombopag doses of 10 mg to 200 mg once daily for 5 days, with geometric mean $AUC_{(0-\tau)}$ values of 302 $\mu\text{g}\cdot\text{h}/\text{mL}$ for the 200 mg once daily regimen. Eltrombopag was well tolerated in healthy subjects at all dose levels.
- In ITP subjects, a dose response was seen for eltrombopag doses of 30 mg to 75 mg once daily, with geometric mean $AUC_{(0-\tau)}$ values of 169 $\mu\text{g}\cdot\text{h}/\text{mL}$ for the 75 mg once daily regimen. There was no significant difference between the safety profile of ITP subjects receiving 30, 50 or 75 mg of eltrombopag. Eltrombopag has been examined in a placebo-controlled Phase II study (NCT00102726) in 183 cancer patients receiving carboplatin and paclitaxel. Eltrombopag, 50 mg, 75 mg and 100 mg and placebo (1:1:1:1) was dosed for 10 days after carboplatin and paclitaxel administration for up to 8 cycles in this study; eltrombopag was generally well tolerated as described in the CIB. The eltrombopag geometric mean $AUC_{(0-\tau)}$ values of 191 $\mu\text{g}\cdot\text{h}/\text{mL}$ was observed for

subjects at 100 mg dose group. The study results for the 100 mg group demonstrated that there was evidence for increased platelet production seen in all three eltrombopag arms after the nadir, with a gradual rise in platelet counts from Day 8 to 18 of chemotherapy. No apparent safety issues at 100 mg were identified.

- Thrombocytosis is a theoretical risk of eltrombopag treatment when high dosages are administered. Thrombocytosis has been observed in healthy volunteers as well as in subjects with ITP. None of these subjects experienced an AE related to thrombocytosis. The likelihood that aplastic anemia patients would develop thrombocytosis, given the underlying pathophysiology of their marrow disease, is likely to be low.
- To ensure subject safety, the current study uses a dose escalation scheme in which subjects are exposed to the lowest dose necessary to achieve the desired platelet count or hemoglobin. Only subjects who have tolerated the previous dose will be considered for the next highest dose, dependent on their last platelet count or hemoglobin. This approach minimizes potential risks while allowing the subject the maximum potential for benefit.
- Our group is currently conducting a clinical trial in patients with severe aplastic anemia using a dosing scheme whereby subjects increase doses by 25mg every 2 weeks. Interim results have shown responses in all 3 lineages with low toxicity. All patients reached the maximum dose of 150mg without any reductions in dose necessary. It is anticipated that it would be similar in MAA population with this revised dosing schedule likely to improve responses.

Dose selection after January 8, 2015:

Starting dose will be 150 mg/day (75 mg/day in East Asian). The dose will be increased by 50 mg/day (25 mg/day Asian) every 4 weeks until subjects reach the maximum dose of 300 mg/day (150mg/day Asian). This will allow reaching the 300 mg dosing at the same time as the previous cohort and generates the least changes in the treatment schema. The rationale for using the half dose for East Asian patients is unchanged; the change in the starting Eltrombopag dose is based on our growing experience with dosing Eltrombopag in bone marrow failure patients (no hematologic response seen at doses lower than 150 mg/day and all patients were increased at least up to 200 mg/day without any side effects) for patients with bone marrow failure syndromes, as well as the recommendation from our DSMB reviewers in 2014. Also, the extended time for each dose, from 2 to 4 weeks will allow for better identification of patients that respond at lower doses than the maximal 300 mg/day.

Pediatric dosing:

For pediatric subjects, there is a predicted higher weight-adjusted drug clearance than older children and adults based upon studies of several drugs approved for use in children, such as anticonvulsants, proton pump inhibitors, theophylline, and HIV protease inhibitors, have routinely demonstrated that young children have higher weight-adjusted drug clearance than older children and adults [Lamictal Package Insert, 2007; Trileptal Package Insert, 2007; Keppra Package Insert, 2008; Prilosec Package Insert, 2008; Kaletra Package Insert, 2007; Viracept Package Insert, 2007; Grygiel, 1983]. The recently published results of a phase II pediatric chronic ITP study (PETIT), subjects between 1 and 5 years received a maximal mean dose of 2.9 mg/kg eltrombopag once daily, while subjects between 6 and 17 years of age received an average daily dose of 57.3 mg daily (13). The maximum dose used in the PETIT trial among all age groups is 75 mg daily dose. In the dose finding part of the study 5 patients was recruited to cohort 3 (ages 1 to 5 years). These subjects initiated dosing with 0.7 mg/kg once daily and increased to at least 1.4 mg/kg once daily by the Week 12 visit. Patients in this cohort received a median of 66mg eltrombopag daily (3mg/kg: range 34-75mg). Preliminary PK data collected for 3 subjects (ages ranging from 2 to 5 years) receiving eltrombopag 1.1 to 1.2 mg/kg once daily at Week 6 suggest that this regimen delivers

plasma eltrombopag exposure similar to a 37.5 to 50 mg once daily regimen in adults. No new pediatric specific safety signal has been identified thus far. The available platelet count, safety, and PK data available for subjects enrolled in the PETIT trial support a starting dose of 2.5 mg/kg once daily for non-Asian subjects aged 2-5 years.

2.7 Rationale for permitting dose interruption

The effect of dose interruption is unknown in the MAA population. In the pooled data from ITP studies TRA100773A and TRA100773B, a total of 11 subjects (10%) treated with eltrombopag and 6 subjects (9%) treated with placebo had a transient decrease in platelet counts (platelet counts <10 Gi/L and at least 10 Gi/L less than baseline platelet count within 4 weeks of eltrombopag discontinuation); generally, the decreases in platelet counts were not associated with clinically meaningful bleeding events. We anticipate some patients on the current trial will be hospitalized for other disease-related issues such as fever and neutropenia during the study, and may require suspension of the study drug temporarily.

2.8 Rationale for extended access to study medication

In patients with refractory cytopenias due to MAA, there is little evidence for spontaneous recovery. There is also little evidence that cytokine drugs such as erythropoietin, G-CSF, or TPO-R agonists have efficacy sustained beyond the treatment period. As this class of agents is cleared from the circulation and metabolized or excreted, new hematopoietic progenitor cells are being produced in the bone marrow and are not exposed to the drug. The impact on production of end-stage cells with life-spans in the circulation, such as red cells, platelets or neutrophils, therefore does not last more than days to weeks beyond cessation of therapy. Study TRA105325 is an open label dose modification extension study evaluating the safety and efficacy of extended therapy of eltrombopag in ITP subjects. As of 2/8/2008, the extent of exposure in this population was as follows: the median daily dose was 50 mg, the median number of days on treatment was 194 days (6.5 months) and the median cumulative dose was 6725 mg. ITP patients have return of their platelet counts to baseline within 1-2 weeks of discontinuation of drug.

We will continue treatment beyond the primary endpoint at 16 or 20 weeks in the current study, in patients responding to the drug. Toxicity and efficacy data will continue to be collected during extended access in order to help identify the secondary endpoints of efficacy, duration of response and toxicities with extended duration of therapy.

We hypothesize, based on our results in patients on the extension phase of other eltrombopag trials conducted at NHLBI that once hematopoietic stem and primitive progenitor cells are normalized in number by exposure to eltrombopag, this increase in number may be able to maintain more normal hematopoiesis without continued exposure to drug, or with exposure to lower doses of drug. We have written parameters to taper and discontinue eltrombopag in the extension studies targeting the lowest dose or duration able to sustain blood counts in a safe and non-symptomatic range.

2.9 Scientific and Clinical Justification of the Protocol

Management of moderate aplastic anemia is similar to that of severe disease and includes immune suppressive therapy (IST), supportive therapy with transfusions or cytokines, or allogeneic transplantation in IST refractory patients. Prophylactic platelets may be essential to prevent bleeding complications and transfusion may be required more than once a week. Red cell transfusion is often necessary up to once or twice every month. There are many potentially serious complications of blood product administration including alloimmunisation, transmission of infectious agents, iron overload, and transfusion reactions. Blood products are expensive and supply is often precarious. New treatment modalities are needed for this population.

Thrombopoietin (TPO) is a potent endogenous cytokine and the principal regulator of platelet production. On binding to TPO receptors on megakaryocyte progenitors, TPO initiates a number of signal transduction events to increase the production of mature megakaryocytes and platelets. A nonpeptide mimetic, eltrombopag, has been shown to increase platelets in healthy subjects and in patients with chronic immune thrombocytopenic purpura (ITP). Eltrombopag is administered orally, well tolerated and does not induce auto-antibodies, in contrast to first-generation TPO-R agonists such as megakaryocyte growth and development factor (MDGF).

In 2 completed efficacy studies in subjects with ITP (TRA100779A/TRA100773B), 62% of subjects responded with a clinically meaningful increase in platelet counts. Eltrombopag induced elevations in platelet counts ≥ 50 K/uL. Clinically significant bleeding (WHO Bleeding Grades 2 to 4) in the eltrombopag 50 mg treatment groups was nearly one-half that observed in the placebo-treatment groups. Summary data indicate in the 269 subjects with ITP who received at least one dose of eltrombopag (from 30 to 75 mg) in either a short-term study (Studies TRA100773A and TRA100773B) for up to 6 weeks or an ongoing open-label study (Studies TRA105325/EXTEND and TRA108057/REPEAT): A dose-dependent increase in platelet count was observed after 5 to 10 day repeat dosing with eltrombopag. Maximum platelet counts were observed approximately 2 weeks after initiating dosing, and returned to within normal limits within 2 weeks after discontinuation of eltrombopag dosing in healthy adult subjects. Transient decreases in platelet counts to levels below baseline were observed in subjects after eltrombopag treatment cycles in REPEAT. However, the decreases in platelet count were not accompanied by clinically meaningful increases in bleeding symptoms. Consistent response to eltrombopag was observed based upon analysis of the primary endpoint in the REPEAT study. Eighty-eight percent of subjects who responded in Cycle 1, responded again in Cycle 2 or 3, with a similar pharmacodynamic response to eltrombopag and a decrease in bleeding symptoms as observed in Studies TRA100773A and TRA100773B. Efficacy data from the EXTEND study show clinically meaningful continuous platelet count elevations $\geq 50,000$ /uL for at least 10 consecutive weeks in the majority of subjects, with 24% achieving continuous elevation of platelet counts $> 50,000$ /uL for more than 6 months and a decrease in bleeding symptoms.

TPO has significant effects on multipotent stem and progenitor cells in vitro and in mouse models. Our previous studies in patients with refractory severe aplastic anemia confirmed that eltrombopag is able to restore trilineage hematopoiesis likely due to its TPO agonistic effect on hematopoietic stem cells. Patients with MAA have less severe manifestations of their disease as a result of better hematopoietic reserve. Despite this, treatment options are limited and there is no licensed agent for specific use in this population. Eltrombopag has a favorable toxicity profile, is administered conveniently as an oral agent and is likely to be efficacious in patients with MAA because of functional albeit reduced hematopoietic reserve.

[figure not shown]
Because trilineage responses can be achieved with this agent bone marrow failure with unilineage cytopenias also have the potential to respond.

3.0 STUDY DESIGN

[figure not shown]
The study is designed as a non-randomized, Phase II, dose modification study of the oral TPO-R agonist eltrombopag in moderate aplastic anemia patients or those with bone marrow failure with unilineage cytopenia. The primary endpoint is measured at 16 to 20 weeks (+/- 7 days). Subjects with evidence for a clinical response in any lineage at 16 weeks but not yet meeting full primary endpoint response criteria, and who are tolerating investigational treatment, may receive an additional 4 weeks of eltrombopag and be reassessed after 20 weeks (+/- 7 days). At that time, if they meet primary endpoint response criteria, they will be eligible to enter the extended access part of the study. If they do not meet primary endpoint response criteria, eltrombopag will be discontinued. Subjects who cannot tolerate the medication or fail to respond by 16 to 20 weeks (+/- 7 days) will go off study. Drug dose during extended access will be at the lowest dosage that maintains stable blood counts or taken off drug for robust response until they meet off study

criteria or the study is closed. If subjects are taken off drug for robust response during extended access and maintain response, they will be taken off study after 3years.

Protocol Schema prior to January 8, 2015:

Protocol Schema after January 8, 2015:

4.0 ELIGIBILITY ASSESSMENT

4.1 Inclusion criteria

4.1.1 Current diagnosis of moderate aplastic anemia **OR** unilineage bone marrow failure disorders.

- **Moderate aplastic anemia is defined** as aplastic anemia (hypocellular bone marrow for age) with no evidence for other disease processes causing marrow failure, and depression of at least two out of three blood counts below the normal values:

- $ANC \leq 1200/mm^3$
- platelet count $\leq 70,000/mm^3$
- anemia with hemoglobin ≤ 8.5 g/dL and absolute reticulocyte count $\leq 60,000/mm^3$ in transfusion-dependent patients

but not fulfilling the criteria for severe disease defined by depression of two of the three peripheral counts:

- $ANC \leq 500/mm^3$

- platelet count $\leq 20,000/\text{mm}^3$
 - reticulocyte count $\leq 60,000/\text{mm}^3$)
 - **Unilineage bone marrow failure disorders are defined:**
 - Hemoglobin < 8.5 g/dL and reticulocyte count $< 60,000$ or red cell transfusion dependent and hypocellular to normocellular bone marrow for age with significantly reduced erythroid precursors.
 - **OR** thrombocytopenia $\leq 30,000/\text{uL}$ or platelet transfusion dependent and hypocellular to normocellular bone marrow for age with reduced megakaryocytes.
 - No evidence of viral or drug suppression of the marrow, dysplasia, or underproduction anemias secondary to B12, folate, iron or other reversible causes.
- 4.1.2 Platelet transfusion dependent is defined as the need for platelet transfusion due to platelet counts of $< 10,000$ /uL with no bleeding (prophylactic transfusion) or $< 20,000/\text{uL}$ with bleeding (therapeutic transfusion). Red cell transfusion dependent is defined as transfusion of greater than 4 units of blood in the 8 weeks prior to study entry.
- 4.1.3 Age ≥ 2 years old
- 4.1.4 Weight > 12 kg

4.2 Exclusion criteria

- 4.2.1 Known Diagnosis of Fanconi anemia
- 4.2.2 Counts that meet criteria for severe aplastic anemia
- 4.2.3 Infection not adequately responding to appropriate therapy
- 4.2.4 HIV positivity
- 4.2.5 Creatinine > 2.5 mg/ dL
- 4.2.6 Bilirubin > 2.0 mg/ dL, including congenital abnormalities in the bilirubin count
- 4.2.7 SGOT or SGPT > 5 times the upper limit of normal
- 4.2.8 Hypersensitivity to eltrombopag or its components
- 4.2.9 Female subjects who are nursing or pregnant or are unwilling to take oral contraceptives or refrain from pregnancy if of childbearing potential
- 4.2.10 Evidence of an active malignant hematological or clonal disorder, or abnormal cytogenetic studies of the bone marrow performed within 12 weeks of study entry
- 4.2.11 Unable to understand the investigational nature of the study or give informed consent and does not have a legally authorized representative or surrogate that can provide informed consent per section 10.5
- 4.2.12 Moribund status or concurrent hepatic, renal, cardiac, neurologic, pulmonary, infectious, or metabolic disease of such severity that it would preclude the patient's ability to tolerate protocol therapy, or that death within 7-10 days is likely
- 4.2.13 Treatment with horse or rabbit ATG or Campath within 6 months of study entry
- 4.2.14 Treatment with cytokines such as G-CSF or Erythropoietin
- 4.2.15 Subjects with known liver cirrhosis in severity that would preclude tolerability of eltrombopag as evidenced by albumin $< 35\text{g/L}$
- 4.2.16 Life expectancy of less than 3 months
- 4.2.17 Patients with an active diagnosis of cancer who have received chemotherapeutic treatment or other specific antineoplastic drugs or radiation therapy within 6 months of study entry
- 4.2.18 Unable to take investigational drug

5.0 TREATMENT PLAN

5.1 Administration of study drug (eltrombopag)

Note: Currently sachets are not available, and the manufacturer is working on a new formulation. However, information regarding the use of sachets for children 2-5 years of age or older children unable to take pills is no longer applicable, because the study did not enroll any subjects that required use of the sachets.

Prior to January 8, 2015

Subjects will initiate study drug at 50mg orally once a day, taken on an empty stomach one hour before or at least two hours after a meal as detailed in section 5.9. Subjects of East Asian ancestry (Japanese, Chinese, Taiwanese and Korean) will initiate study drug at 25 mg orally once a day.

After January 8, 2015

Subjects will initiate study drug at 150 mg orally once a day, taken on an empty stomach one hour before or at least two hours after a meal as detailed in section 5.9. Subjects of East Asian ancestry (Japanese, Chinese, Taiwanese and Korean) will initiate study drug at 75 mg orally once a day. Pediatric patients will be treated in a separate cohort with a fixed dose (see Pediatric Dosing table below in section 5.2 and section 10.2).

5.2 Dose Escalation of Eltrombopag Through Primary Endpoint at 16-20 Weeks (See section 2.5)

Patients will be enrolled on study because of anemia and/or thrombocytopenia. The majority of patients are expected to have cytopenias in both lineages, however some patients will have normal or close to normal counts in one or the other lineage at baseline. Therefore, dose escalation criteria will vary depending on whether one or both lineages meet inclusion criteria. Escalation will occur via the tables below and continue to the maximum dose until the inclusion criterion lineage or lineages responds, according to the schema set out below, unless toxicity-related stopping or dose reduction lab values occur. Note that patients entering the study based on anemia, with normal or near normal platelet count, will be expected to have an increased in their platelet count on eltrombopag, but dose escalation for anemia will not be halted unless the platelet count goes above 400,000/uL. For patients entering meeting both anemia and thrombocytopenia eligibility criteria, dose escalation will not stop until both lineages reach the thresholds given below to stay on the current dose, unless platelets go over 400,000/uL or hemoglobin goes over 16.0 gr/dL, in which case drug will be discontinued for one week and the dose decreased by 50%.

Dose Escalation for Patients Entering with Platelets <30,000/uL or transfusion-dependence:

Platelet Count < 30,000/uL or transfusion-dependent at baseline	Dose Adjustment or Response
<20,000/uL above baseline	Increase daily dose by 50 mg (25 mg for East Asians) every 4 weeks to maximum 300 mg/day for non- East Asians (150 mg/day for East Asians).
≥20,000/uL above baseline but ≤200,000/uL following at least 2 weeks of eltrombopag	Keep at current dosage.
>200,000/uL (untransfused) at any time on	Decrease dosage by 50 mg (25

Platelet Count < 30,000/uL or transfusion-dependent at baseline	Dose Adjustment or Response
study	mg for East Asians) every 4 weeks to lowest dosage that maintains platelet count $\geq 20,000/uL$ above baseline.
>400,000/uL (untransfused) at any time on study	Discontinue eltrombopag for one week, if platelets < 20,000/uL; restart at 50% of current dose.

Dose Escalation for Patients Entering with Anemia (Hb < 8.5gr/dL or transfusion-dependence)

Hemoglobin < 8.5 gr/dL or transfusion dependent at baseline	Dose Adjustment or Response
Hemoglobin rise of < 1.5 g/dL.	Increase daily dose by 50 mg (25 mg for East Asians) every 4 weeks to maximum 300mg/day for non- East Asians (150mg/day for East Asians).
$\geq 1.5g/dL$ above baseline but $\leq 15g/dL$ following at least 2 weeks of-eltrombopag	Keep at current dosage.
>15g/dL (untransfused) at any time on study	Decrease dosage by 50% to lowest dosage that maintains Hb $\geq 1.5g/dL$ above baseline.
>16g/uL (untransfused) at any time on study	Discontinue eltrombopag for one week, if Hb<15g/dL restart at 50% of current dose. Phlebotomy may be performed if clinically indicated as determined by the investigator.

If after 16 to 20 weeks of treatment there is no response, treatment will be discontinued and subjects will go off study per section 8.6.

Dosing for pediatric patients:

Age groups	Daily dose
Non-Asian	
12-18	150 mg
6-11	75 mg
2-5	2.5 mg/kg
East Asian, South East Asian	
12-18	75 mg
6-11	37.5 mg
2-5	1.25 mg/kg

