5.4 Dose delays, modifications or discontinuation for hematologic side effects

5.4.1 Thrombosis/Embolism: Subjects who experience a deep venous thrombosis or a pulmonary embolus, a TIA or stroke, or a myocardial infarction at any time while on eltrombopag will discontinue the drug and go off study. Patients with platelet counts of > 50,000/uL at the time of thrombosis will be treated with enoxaparin or another appropriate anticoagulant as clinically indicated until the platelet count drops below 20,000/uL with discontinuation of eltrombopag. They will be treated for the thrombotic event as otherwise clinically-indicated.

5.4.2 Evidence for disease progression: The presence of persistent morphologic abnormalities (red cell teardrop forms; immature blast cells) or the development of significant worsening of anemia (requiring transfusions) or neutropenia while on study will require discontinuation of eltrombopag and performance of a bone marrow examination to assess for development of abnormal fibrosis or progression to MDS or AML.

Any morphological changes in the bone marrow fulfilling current WHO criteria for MDS or cytogenetic abnormalities indicating clonal hematopoiesis will require discontinuation of eltrombopag.

5.4.3 Thrombocytosis or erythrocytosis: Patients will have eltrombopag discontinued for one week if platelets increase to >400,000/uL or Hb to > 16 gr/dL, and if counts have fallen below these cutoffs, drug can be restarted at 50% dosage.

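### After a hold for platelets above 400,000/uL, the Section 5.2 table allows restart only below 20,000/uL, which is below its own maintenance target and differs from Section 5.4.3; 20,000 is probably a slip for 200,000

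*Combined protocol and SAP*

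**What the plan says.** The protocol describes the response to an excessive platelet count in three places.

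- **Section 5.2, platelet table.** This covers patients who enter with platelets below 30,000/uL or transfusion-dependent. Two rows matter. The step-down row, ">200,000/uL (untransfused) at any time on" study, reduces the dose "every 4 weeks to lowest dosage that maintains platelet count" at least 20,000/uL above baseline. The hold row, for untransfused counts above 400,000/uL, reads: "Discontinue eltrombopag for one week, if platelets < 20,000/uL; restart at 50% of current dose".
- **Section 5.2, text before the tables.** For patients who qualify on both anemia and thrombocytopenia, platelets over 400,000/uL or hemoglobin over 16.0 g/dL end escalation, "in which case drug will be discontinued for one week and the dose decreased by 50" percent. This sentence gives no restart count.
- **Section 5.4.3.** The one-week hold has the same triggers, platelets above 400,000/uL or hemoglobin above 16 g/dL. Then, "if counts have fallen below these cutoffs, drug can be restarted at 50% dosage".

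The Section 5.2 hemoglobin table has the same structure. Its step-down row applies at ">15g/dL (untransfused) at any time on study", and its hold row, at a value above 16, says: "Discontinue eltrombopag for one week, if Hb<15g/dL restart at 50% of current dose".

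**The concern.** The hold row deals with over-response, yet it withholds drug until the patient has almost no platelets. Section 4.1.1 uses 20,000/mm³ or less as one of the count criteria for severe disease, and Section 4.1.2 uses below 20,000/uL with bleeding as a platelet-transfusion criterion. A rule meant to limit thrombocytosis should not require that level before re-treatment at half dose.

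Section 5.4.3 sets a very different condition for the same event, and no precedence is stated. Two investigators with the same patient could act differently, and each could cite the protocol. The table also does not say what to do if its condition is unmet after the week. The rule applies at any time on study, and Section 5.5 carries the Section 5.2 dosing criteria into extended access, so it is not confined to the first 16 to 20 weeks.

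**Working it through.** No sample size, power or error-rate figure depends on this rule. The check is a comparison of printed thresholds.

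**Step 1: restart value against the table's own target.** Let *b* be the baseline platelet count. The maintenance floor is *b* + 20,000/uL. For entry counts from 0 to below 30,000/uL the floor runs from 20,000 to below 50,000/uL. A restart count is below 20,000, and 20,000 ≤ *b* + 20,000 for every *b* ≥ 0. The restart count is therefore always below the floor, by more than *b*.

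| Baseline (/uL) | Floor (/uL) | Restart count is below floor by | Restart count against baseline |
|---|---|---|---|
| 10,000 | 30,000 | more than 10,000 | may be above or below |
| 25,000 | 45,000 | more than 25,000 | more than 5,000 below |

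**Step 2: table against Section 5.4.3.** The trigger is the same, above 400,000/uL. The table restarts below 20,000 and Section 5.4.3 below 400,000. Counts from 20,000 to just under 400,000/uL fail the first condition and meet the second. The thresholds differ by 400,000 / 20,000 = 20-fold. From 400,000, the table requires a fall of more than (400,000 − 20,000) / 400,000 = 95%.

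**Step 3: what was probably meant.** The two tables side by side:

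| | Step down above | Hold above | Restart below |
|---|---|---|---|
| Hemoglobin (g/dL) | 15 | 16 | 15 |
| Platelets (/uL) | 200,000 | 400,000 | 20,000 |

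Hemoglobin restarts at its own step-down value. The same pattern for platelets gives 200,000/uL, which is one zero more than the printed figure. The hemoglobin hold row has a slip of its own: its trigger is printed per uL instead of per dL.

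**Step 4: what remains if 200,000 is substituted.** The required fall becomes more than (400,000 − 200,000) / 400,000 = 50%. The table and Section 5.4.3 then differ only from 200,000 to just under 400,000/uL, a factor of 400,000 / 200,000 = 2. For hemoglobin the existing difference is 16 − 15 = 1 g/dL. Correcting the one figure therefore narrows the mismatch but does not remove it.

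**Step 5: would the printed condition be met after one week?** The only one-week off-drug figure in the protocol is from the ITP repeat-dose study (Section 2.4.6), where median platelets were still above 100,000/uL one week after stopping. That is a different disease, and Section 2.7 says the effect of interruption in MAA is unknown. It suggests, without proving, that the printed condition would often be unmet at the one-week check.

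**The case against.** The strongest reply is that the two sections can both be obeyed. Section 5.4.3 permits restart and does not require it, so a site that waits for the stricter table value breaches nothing. That is correct, and it limits the consequence. The reverse does not hold: restarting at 150,000/uL satisfies Section 5.4.3 and departs from the table.

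A second reply is that a restart condition need not lie inside the maintenance band. Section 5.5 allows re-initiation in extended access when counts fall below entry values or platelets fall below 30,000/uL. That rule, however, follows a planned stop for a robust or stable response, not a one-week hold that leads to half dose, and its platelet trigger is still above 20,000.

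Third, the intended figure is not certain. Omitted words (a count relative to baseline) or an intended 400,000/uL are also possible. A literal reading can work for some patients too: Section 2.8 reports that ITP counts return to baseline within one to two weeks of stopping, so a patient with a baseline under 20,000/uL might qualify. The slip is an inference, but the inconsistency does not depend on it.

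Fourth, taken alone the Section 5.2 text for patients with both cytopenias would allow restart at any count. The table and Section 5.4.3 both supply a count condition, so little weight belongs on this.

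Last, Section 9.2.1 lets investigators interrupt dosing at their discretion without reporting a deviation, and the past-tense note on sachets in Section 5.1 hints that accrual was well advanced. Both reduce the practical reach. Neither gives a restart threshold.

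**Conclusion.** The concern holds. The printed restart value is below the table's own target for every baseline and differs 20-fold from Section 5.4.3, with no order of precedence. This is a dosing-safety threshold that is wrong as written and should be fixed.

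Its consequences are limited. The protocol itself says: "The likelihood that aplastic anemia patients would develop thrombocytosis, given the underlying pathophysiology of their marrow disease, is likely to be low". Dose reduction already starts at 200,000/uL, so few patients are likely to reach the hold; the number cannot be derived from the documents. An effect on an individual's week-16 or week-20 response is possible but not shown. Confidence in the inconsistency is high. That 200,000/uL was intended is probable and needs the sponsor's confirmation.

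**What to change.** 1. Replace the restart value in the platelet hold row: below 200,000/uL if the sponsor confirms the slip, otherwise the Section 5.4.3 value of below 400,000/uL.
2. Use that same platelet threshold, and a single hemoglobin threshold (15 or 16 g/dL), in both the Section 5.2 tables and Section 5.4.3.
3. Have the Section 5.2 text for patients with both cytopenias refer to that one rule.
4. State what happens if the threshold is not met after one week, for example continued hold with a repeat count at a stated interval.

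This is a wording amendment only. Sample size, visit schedule and analysis do not change.
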